13.5 Analysis of Exploratory Endpoints

To determine the effect of combination therapy with CDX-1127 (varlilumab) and nivolumab on the immune system as assessed by immunohistochemistry (IHC), mass cytometry (CyTOF) and changes in serum cytokine profile, multiple measures will be evaluated. For each measure below, baseline values and changes in these parameters over time will be both graphically and quantitatively summarized and explored. Standard paired comparisons methodologies (Wilcoxon signed rank and McNemar's tests) will be used to assess changes in these variables before and after therapy. In addition, baseline values and changes over time in each measure will be explored in relation to clinical outcome. Differences between responders and non-responders will be assessed using Wilcoxon's rank sum (continuous data) or Fisher's exact (categorical data) test. The relationship between each measure and time to event measures (PFS, OS) will be evaluated using Cox's proportional hazards models and log-rank tests.

CD27 IHC: CD27 expression will be evaluated in terms of level (an ordinal • variable such as low, medium, high), % of cells expressing, and location (expression in tumor cells vs. expression in normal immune cells). The expression level can be gathered continuously and may also be evaluated as a categorical variable (low, medium, high expression for example). These values will be evaluated as predictors of response. This is the only integrated biomarker. The expression level of CD27 will be analyzed using the "marker-by-treatment predictiveness curves" in Janes et al. to explore CD27 as a potential predictive biomarker for the benefit of Varlilumab. Specifically, we will display the response rate as a function of the percentiles of CD27 for each treatment arm: Varlilumab plus Nivolumab and Nivolumab alone. We will use logistic regression to model the response rate as a function of treatment and CD27 (as a continuous variable). The distribution of CD27 will be estimated empirically in the entire trial population and used to calculate CD27 values corresponding to each fixed percentile. If the two predictiveness curves cross (suggesting predictive potential of CD27), the point where the two curves cross would be a possible choice of threshold for dichotomizing CD27 into "low" versus "high". Threshold levels

shown to be best predictors of clinical outcomes will be considered as reference for later pivotal trials.

- Analysis of Peripheral Blood Immune cells by Mass Cytometry (CyTOF): The patient's peripheral blood will be evaluated serially (at baseline and every 14 days for the first 12 weeks on study). The assay will detect and quantify the presence of specific subpopulations of immune cells (expressed as % of parent). In this exploratory analysis the relationship between presence/absence of a particular subtype of cell and association with outcomes will be evaluated. Evaluation of particular combinations of immune cells (immune signature) and whether they are predictive of outcome will also be evaluated.
- Identification/Characterization of Intratumoral Immune cells by IHC and CyTOF: Immune cell subpopulations in the neighborhood around the tumor will be evaluated with this assay. This is similar to above (CyTOF on peripheral blood) but in this case the assessment is made on the tumor biopsy specimen. The presence/absence of different subsets will be identified and quantified and the association with clinical outcomes will be evaluated as specified above. This is another exploratory biomarker.
- Evaluation of Genetic Alterations of Chromosome 9p24.1 by FISH: This chromosomal region will be evaluated and patients will be categorized in 4 groups: normal, amplified, relative copy gain or polysomy. The proportion of patients in each of these groups who achieve a response will be evaluated. This is another exploratory biomarker.
- Evaluation of Serum Cytokine Profile by ELISA: Serially collected peripheral blood (at baseline and every 14 days for the first 12 weeks on study) will be analyzed. The levels (continuous variable) of 30 different cytokines will be assessed at each of those time points. The elevation or decrease in any individual cytokine or a combination of them will be explored, as well as the association with outcomes. This is another exploratory biomarker.
- Evaluation of Mutation Burden by WES: Tumor tissue will undergo whole-exome sequencing to determine if the amount of mutations (continuous) is associated with outcome. This is another exploratory biomarker.

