1.3 Exploratory Objectives

- 1.3.1 To determine the effect of combination therapy with CDX-1127 (varlilumab) and nivolumab on the immune system as assessed by immunohistochemistry (IHC), mass cytometry (CyTOF), changes in serum cytokine profile and immunogenicity assays.
- 1.3.2 To describe the pharmacokinetic profile of CDX-1127 (varlilumab) and nivolumab when used in combination.

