3.2 Exclusion Criteria

3.2.1 Patient has received chemotherapy, targeted agent, or radiotherapy within 4 weeks or at least 5 half-lives, whichever is longer, prior to registration.

Palliative (limited-field) radiation therapy is permitted, if all of the following criteria are met:

- 1) Repeat imaging demonstrates no new sites of bone metastases.
- 2) The lesion being considered for palliative radiation is not a target lesion.
- 3.2.2 Patient has received immunotherapy (including monoclonal antibodies) within 4 weeks prior to registration.
- 3.2.3 Patients who have not recovered to grade 1 or less from any adverse events due to agents administered more than 4 weeks earlier (excluding alopecia)
- 3.2.4 Patients who are receiving any other investigational agents.
- 3.2.5 Patients should be excluded if they have had prior treatment with an anti-PD-1, anti-PD-L1, anti-PD-L2, anti-CTLA-4 antibody, or any other antibody or drug specifically targeting T-cell co-stimulation or immune checkpoint pathways.
- 3.2.6 Patients who have received autologous stem cell transplant (ASCT) \leq 12 weeks prior to the first dose of study drug.
- 3.2.7 Patients with a prior history of allogeneic stem cell or solid organ transplantation.
- 3.2.8 Patients with evidence of active disease in the central nervous system (CNS) defined as either the presence of active lesions on MRI obtained within 4 weeks of registration or progressive neurological decline.

Patients with primary CNS lymphoma who develop systemic recurrence following standard therapy may be included as long as no active CNS disease is present at the time or enrollment. Similarly, patients with secondary involvement of the CNS from a systemic lymphoma may be included as long as the CNS disease has been optimally treated and they demonstrate no evidence of active CNS disease.

3.2.9 History of allergic reactions attributed to compounds of similar chemical or biologic composition to CDX-1127 (varlilumab) and/or nivolumab.

- 3.2.10 History of severe hypersensitivity reaction to any monoclonal antibody.
- 3.2.11 Uncontrolled intercurrent illness including, but not limited to, ongoing or active infection, symptomatic congestive heart failure, unstable angina pectoris, cardiac arrhythmia, or psychiatric illness/social situations that would limit compliance with study requirements.

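### Section 13.5 tests change in the immune measures only before versus after therapy and plans no comparison of that change between the randomised groups, although both groups give the same serial blood samples

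*Combined protocol and SAP*

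**What the plan says.** Objective 1.3.1 is "To determine the effect of combination therapy with CDX-1127 (varlilumab) and nivolumab on the immune system", assessed by IHC, CyTOF, serum cytokines and immunogenicity assays. Section 13.5 repeats the aim for all but immunogenicity and then names its tests:

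- Change over time: paired tests (Wilcoxon signed rank and McNemar), which "will be used to assess changes in these variables before and after therapy".
- Association with response: "Differences between responders and non-responders will be assessed using Wilcoxon's rank sum (continuous data) or Fisher's exact (categorical data) test".
- Association with survival outcomes: "The relationship between each measure and time to event measures (PFS, OS) will be evaluated using Cox's proportional hazards models and log-rank tests".

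Section 13.5 also plans graphical and numerical summaries of change, without saying whether they are split by arm. Treatment arm enters the section once, in the CD27 predictiveness curves. There response is the outcome and CD27 is a predictor.

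The blood schedule is common to both groups. Sections 9.1 and 13.5 set CyTOF and cytokine draws at baseline and every 14 days for 12 weeks. Appendix E lists the same two ACD tubes, and at least one red-top tube, for Groups 1 and 2 at every draw through C3D15. (Section 2.4.2.1 mentions 24 weeks for the CyTOF blood; this point uses the 12-week schedule.)

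**The concern.** A change from before to after therapy has several possible sources, and a paired test adds them together.

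- **Nivolumab.** Both groups receive it (Section 5.1).
- **Recovery from earlier treatment.** Section 3.2 sets the exclusion as "Patient has received immunotherapy (including monoclonal antibodies) within 4 weeks prior to registration". For chemotherapy, targeted agents and radiotherapy the limit is 4 weeks or 5 half-lives, whichever is longer. For systemic steroids above 10 mg prednisone equivalent it is 14 days. Cell subsets and cytokines could still be moving at entry.
- **Time trends**, including progression.
- **Varlilumab**, the only component that differs between the groups.

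The randomised nivolumab-only group is the means of separating varlilumab from the rest. It is sampled, but no planned test of marker change uses it. If the paired tests are pooled, changes on nivolumab alone would also enter a result reported under an objective about the combination.

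At stake is the reading of the biomarker results. A marker could be reported as changed on the combination when it changes equally on nivolumab alone. A varlilumab effect that offsets a nivolumab effect could be missed.

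**Working it through.** **1. The plan's own figure.** Section 13.5 states no sample size or power, so 48 per group is taken from Section 13.1.3 (25% versus 45% response, one-sided 0.15, 80% power). This reproduces. The two-proportion formula gives 40 per group, or 49 with continuity correction. Exact enumeration of the one-sided Fisher test at 48 per group gives 80.9% power.

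**2. Is a between-arm test of marker change planned anywhere?** In Section 13.5 the rank-sum and Fisher tests group patients by response, the Cox and log-rank analyses relate markers to PFS and OS, and the CD27 model has response as its outcome. The marker-specific bullets and Section 9.3 add no contrast by arm. By comparison, Sections 13.4.1 to 13.4.3.1 compare duration of response, survival, PFS and grade 3 or higher adverse events between arms explicitly.

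**3. Do the draws precede crossover?** C3D15 is day 2 × 28 + 15 = 71. The first scheduled scan is 12 weeks from C1D1 (day 85), with a window of 3 days, so day 82 at the earliest. On schedule, every CyTOF and cytokine draw comes before it. Section 5.1 allows crossover at progression at any time, so a few patients may cross over sooner.

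**4. Illustration of size.** The documents give no SD, effect size or significance level for these markers. Assumptions: normal change scores with SD 1, 48 evaluable per arm, two-sided 0.05, no varlilumab effect, and a shift common to both arms. Simulation, 4,000 runs per setting:

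| Common shift (SD) | Paired signed-rank test within Group 2 significant | Between-arm rank-sum test of change significant |
|---|---|---|
| 0 | 4.8% | 4.9% |
| 0.25 | 37.7% | 4.6% |
| 0.5 | 91.2% | 5.0% |
| 0.75 | 99.95% | 5.0% |
| 1.0 | 100% | 5.5% |

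Hand check, with rank efficiency 3/π = 0.955: paired power ≈ Φ(d√(0.955n) − 1.96). For d = 0.5 and n = 48 this is Φ(0.5 × 6.770 − 1.96) = Φ(1.425) = 92%.

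**5. What the between-arm test can detect.** Simulated power with 48 per arm is about 47%, 65%, 81% and 90% for a true added shift of 0.4, 0.5, 0.6 and 0.7 SD. Hand check at 0.6: Φ(0.6 × √(0.955 × 24) − 1.96) = Φ(0.912) = 82%. For 80% power the detectable shift is 2.802 / 6.770 = 0.41 SD within one arm and 2.802 / 4.787 = 0.59 SD between arms.

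**6. Which draw?** Section 2.2.1 gives a varlilumab half-life of 6 days at 1 mg/kg and 10.6 days at 10 mg/kg. Under simple exponential decay the fraction of one dose remaining is 2^(−t/half-life). At 14 days (C1D15) that is 20% to 40%. At 28 days (C2D1, before the second dose) it is 4% to 16%. The choice of draw therefore affects how much of a short-lived effect could be seen.

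**7. Tumour markers.** A post-baseline biopsy is mandatory only for Group 1 patients who cross over, and it is taken after nivolumab alone. Other biopsies at progression are optional and expected in about 25% of patients (Section 9.1). No sound randomised contrast of change is available there.

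**The case against.** The strongest reply is that objective 1.3.1 does not ask for the contrast. Objective 1.1.1 says the comparison is with nivolumab alone; 1.3.1 does not. The combination includes nivolumab, so a nivolumab-driven change in Group 2 is part of its total effect. This stands. A reader might infer that the paired tests would produce false findings at the simulated rates, or that the objective goes unanswered. The documents do not support either inference: where the common shift is due to nivolumab, those rejections are true findings under the literal wording.

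It is also true that Section 13.5 does not place the paired tests in Group 2. It is silent on arm and does not rule out summaries by arm, so one cannot say that the combination will be credited with a nivolumab effect.

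Finally, Section 9.1 calls the correlative work other than CD27 IHC exploratory and hypothesis-generating, several assay sections say the results will be largely descriptive, and no decision rule in Sections 13.1.3 or 13.7 uses them. This lowers the severity.

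Three things remain. Recovery and time trends are unseparated on either reading of the objective. The trial's hypothesis in Section 2.3.1 is synergy compared with single-agent nivolumab, which makes varlilumab's added effect the natural question. And exploratory status does not make an uncontrolled before-after test sound when a randomised control is already sampled.

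**Conclusion.** The point holds as a minor one. Section 13.5 tests marker change only by paired comparisons, leaves open whether they are by arm or pooled, and makes no use of the randomised groups for marker change. As written, it cannot separate drug effect from recovery or time trend, or varlilumab's contribution from nivolumab's.

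Its size in this trial is unknown. The percentages rest on assumed shifts of 0 to 1 SD, normal change scores, a 0.05 level and 48 evaluable per arm. They show how the two tests behave and do not estimate error here. The claim that the data to answer the question are already collected is true only of the serial blood markers.

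**What to change.** Add to Section 13.5, for the CyTOF blood subsets and serum cytokines only:

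- **A between-group analysis** of change from baseline, with confidence intervals, using the scheduled pre-crossover draws through week 12. A baseline-adjusted repeated-measures model would serve. So would a rank-sum test at one pre-named draw, chosen with the varlilumab dosing interval in mind.
- **A rule for draws after early crossover**, for example that they do not enter the comparison, and a statement of the missing-data assumption this implies.
- **The paired tests run separately by arm** and labelled as within-arm description.
- **Emphasis on estimates and intervals.** With 30 cytokines at an assumed 0.05 level, 30 × 0.05 = 1.5 nominal findings per draw are expected by chance.

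State that change in tumour markers stays descriptive, because post-baseline biopsies are mandatory only for Group 1 crossover patients.

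The cost is some SAP wording and a few lines of code, with no new samples, visits or patients. The downside is lower sensitivity (about 0.59 SD detectable between arms against 0.41 SD within an arm, under the assumptions above), so fewer markers will be declared changed.

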13.1.3 Statistical Design

Decision Rule: A randomized trial comparing combination therapy with CDX-1127 (varlilumab) and nivolumab as compared to nivolumab alone will be conducted as described by Rubinstein. We will enter 48 evaluable patients on each group of the study using a 1:1 randomization scheme where patients are stratified based on age (< 65 vs. \geq 65 years), previous autologous stem cell transplant (yes vs. no), and diagnosis category per Section 3.1.1 (A vs. B). Randomization will be done using a (stratified) permuted block design with randomly varying block sizes. A sample size of 48 patients per group provides 80% power to detect an improvement in response rate from 25% to 45%, using a one-sided test at a significance level of 0.15 (nQuery 7.0).

This estimated response rate is based on the clinical efficacy demonstrated by Nivolumab in the phase II trial (Lesokhin et al, JCO 2016). In that study 11 patients with DLBCL were treated with Nivolumab, of which 4 (36%) achieved an objective response. Nonetheless, at the time of publication only 1 of those maintained a response while 2 were still being followed (3 of 11 or 27%). Unpublished data from a larger phase 2 trial appears to have a low response rate for nivolumab alone with an overall response rate that appears to be < 20%. We therefore selected 25% as our best estimate of response for nivolumab alone.

Interim Analysis Decision Rule: An interim analysis with a futility rule will be performed after half of the patients (24 patients in each group) have completed their first radiologic scan after 3 cycles (12 weeks of treatment or up to 20 weeks if treatment delays occurred). At the time of the interim analysis, we will compare the response rate of Group 2 the experimental group to Group 1 the control group. If the response rate in Group 2 the experimental group is less than the response rate in Group 1 the control group, we will consider this early evidence that the Group 2 the experimental group does not have a higher overall response rate and accrual will be terminated. Otherwise, we will continue accrual (Wieand *et al.*, 1994)

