13.1.5 Primary Endpoint

Definition: The primary endpoint of this trial is the overall response rate, which will be compared between the two arms. A response will be defined as an objective status of PR or CR for patients evaluated by CT-based criteria and CMR or PMR for patients evaluated by PET-CT based criteria. All patients meeting the eligibility criteria who have signed a consent form and have begun treatment will be evaluable for overall response.

Estimation: The proportion of successes will be estimated in each arm by the number of successes divided by the total number of evaluable patients. Exact binomial ninety-five percent confidence intervals for the true success proportion will be calculated in

each arm. Comparison of overall response rates between the two treatment groups will be performed using a one-sided Fisher's exact test at significance level 0.15.

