13.2 Sample Size/Accrual Rate

13.2.1 Sample Size

A maximum of 96 evaluable patients (48 in each group) will be accrued unless undue toxicity is encountered. We anticipate accruing an additional 10 patients to account for ineligibility, cancellation, major treatment violation, or other reasons. Maximum projected accrual is 106 patients.

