13.4.3 Progression Free Survival

Progression free survival is defined as the time from randomization to the earliest

date of documentation of disease progression (PMD or PD) or death due to any cause. The distribution of progression-free survival will be estimated using the method of Kaplan-Meier. The comparison of progression-free survival between two treatment arms will be based on the log-rank test.

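### Section 13.5 relates on-treatment biomarker change to PFS and OS timed from randomisation without a landmark or fixed draw, so some permitted summaries can make a null marker look protective

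*Combined protocol and SAP*

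**What the plan says.** Section 13.5 states that "baseline values and changes over time in each measure will be explored in relation to clinical outcome", and then: "The relationship between each measure and time to event measures (PFS, OS) will be evaluated using Cox's proportional hazards models and log-rank tests". Both clocks start before any change can be seen. In 13.4.3, "Progression free survival is defined as the time from randomization to the earliest" documented progression or death, and 13.4.2 also times survival from randomisation.

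**Sampling.** Sections 9.1 and 13.5 have blood for CyTOF and 30 cytokines taken at baseline and every 14 days for 12 weeks. The calendar in Section 10 places the draws in weeks 1, 3, 5, 7, 9 and 11, and its footnote f ties them to dosing days, before the dose. Section 5.3 ends treatment at progression, except for Group 1 patients who cross over. Section 9.1 makes blood at progression optional. Section 11.1.1 foresees progression even before the end of cycle 1.

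**What is not fixed.** Section 13.5 does not say how change is to be summarised. Its cytokine item speaks of a rise or fall in any cytokine or combination, with no time point. No section gives a landmark, a time-dependent covariate, or a rule for patients who fail inside the sampling window.

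**The concern.** A patient who fails in week 5 contributes one or two post-dose draws; one who passes week 11 contributes five. Any summary that tends to grow with the number of draws, or with time on treatment, then carries information about PFS even when the marker has none. This is immortal-time (guarantee-time) bias, and here it runs one way: larger change, longer PFS.

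The same mechanism reaches the responder versus non-responder comparisons in 13.5, because early failures are non-responders with fewer draws. Its size there was not calculated.

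Section 9.1 presents this work as hypothesis-generating. A one-directional artefact that can recur across 30 cytokines and many cell subsets would send the wrong markers forward.

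**Working it through.** **The plan's own figure.** The plan gives no error rate for these analyses. Its only stated operating characteristic is for the primary endpoint: 48 per group, 25% v 45%, "one-sided Fisher's exact test at significance level 0.15", 80% power. With z values 1.036 and 0.842, n = [1.036√(2×0.35×0.65) + 0.842√(0.25×0.75 + 0.45×0.55)]² / 0.20² ≈ 39.3, so 40 per group, or 49 with continuity correction. Exact Fisher power at 48 per group is 80.9%. The figure reproduces and is not affected by this point.

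**Inputs from the documents.** 96 evaluable patients (13.2.1). The week-1 draw is pre-dose, so there are five post-dose draws, 2, 4, 6, 8 and 10 weeks after the first dose. PFS and OS run from randomisation.

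**Assumptions (not in the documents).** Exponential PFS with the medians shown below; a marker unrelated to outcome; no draws after progression or death; Cox score test at two-sided 5%.

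**Mechanism.** Call a marker raised if any change exceeds 1 SD, with independent changes. One draw gives probability 0.159. Five draws give 1 − 0.841⁵ ≈ 0.58. Survival through the window alone moves a null marker from 16% to 58% raised.

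**Share failing before week 12.** 1 − 0.5^(12/median): 65%, 50% and 27% at medians of 8, 12 and 26 weeks; 62%, 47% and 27% at 2, 3 and 6 months.

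**False-positive rate for PFS, every early progression found when it occurs**

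| Summary of change | Set-up | Median PFS | Rate |
|---|---|---|---|
| Maximum | changes share one noisy baseline | 8 / 12 / 26 weeks | 47 / 35 / 17% |
| Maximum | changes independent | 2 / 3 / 6 months | 87 / 70 / 39% |
| Ever raised | changes independent | 2 / 3 / 6 months | 83 / 65 / 34% |
| Maximum | random-walk changes | 3 months | 23% |
| Last available / mean | marker drifts up 1 SD over 10 weeks | 3 months | 34 / 40% |
| Last available | no drift | 2–6 months | 5–6% |
| Mean | no drift | 2–6 months | up to 11%, hazard ratio unshifted |
| One fixed week, patients still sampled | all set-ups | 2–6 months | 3.7–6.3% |

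The first row used 4,000 trials per scenario and the others 2,000. Repeat runs of the first row gave 46–50%, 32–34% and 14–16%. Shared baseline noise explains the gap between the first two rows. Nearly all false positives for maximum and ever-raised change are in the protective direction.

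**Effect of the 12-weekly scan (maximum change, PFS).** With half of early progressions found before the scan, the shared-baseline set-up gives 14–17% at 8 weeks and 8–13% at 12 weeks. Independent changes give about 33% at 12 weeks to 3 months, falling at 3 months to 10% with a fifth found early and 5% with none.

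**OS.** Maximum change gives 23 / 20 / 15% at PFS medians of 2 / 3 / 6 months, with assumed post-progression medians of 4, 6 or 9 months, all early failures detected and no drift.

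**After the fix.** A landmark at the draw 10 weeks after the first dose gives 4.6–5.5% for PFS. Change at 4 weeks with the clock restarted there gives 4.6–5.9%. A week-12 landmark with maximum change gives 4.9–6.7% for PFS and 4.2–6.5% for OS, with hazard ratios of 0.99–1.01.

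**The case against.** The strongest reply is that the biased statistic is not in the plan. Section 13.5 says only that changes over time will be explored, and it measures cytokine levels at each time point. Change at one fixed week, or the last available change of a marker without drift, keeps the nominal rate. This stands: the plan under-specifies, and a reader who infers that it produces false associations as written goes further than the text. What remains is that the cytokine wording permits the biased summaries, and Section 2.4.2.4 reports that pro-inflammatory cytokines rose in the earlier trials, which is the drift that also biases last and mean change.

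Second, scans are 12-weekly (11.1.3), after the last draw in week 11. Section 11.1.4 classes some early growth without clinical deterioration as indeterminate, and such patients may stay on treatment. This also stands, and it cuts the bias sharply. It does not remove it, because unscheduled imaging, clinical progression and death inside the window are all provided for.

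Third, a reader might infer that longer survival keeps adding measurements, or that OS is as exposed as PFS. Neither holds. No serial draws are scheduled after about week 11, Section 3.1.6 requires life expectancy above 12 weeks, and the simulated OS rates are well below those for PFS.

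Fourth, cytokine and CyTOF results are labelled exploratory and largely descriptive. That lowers the priority. It excuses low power and multiplicity, but not a known directional bias that wording can remove.

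**Conclusion.** The concern holds in limited form. The draw schedule, the stop at progression and the clock from randomisation together leave 13.5 open to immortal-time bias, and no safeguard is stated. Whether it occurs depends on the summary chosen.

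For maximum change, 47%, 35% and 17% false positives at assumed median PFS of 8, 12 and 26 weeks are an upper case on detection timing. A more realistic range is roughly 8–17% at 8–12 weeks with half of early progressions found before the scan and a shared noisy baseline, or about 33% at 12 weeks with independent changes. The rate nears 5% if few are found early. These figures rest on exponential PFS and assumed medians; the documents give none.

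It would be wrong to infer that the whole biomarker programme is compromised. Baseline-value analyses, the CD27 predictiveness curves on registration tissue (9.2.1.4) and the primary endpoint are unaffected. Low-to-moderate priority.

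**What to change.** Add to 13.5:

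- Define change at a pre-specified draw, for example week 5, with the last scheduled draw (week 11) as a second, each with a window for dosing delays.
- Relate it to PFS and OS by a landmark analysis at that draw. Include only patients alive, progression-free and sampled then, and count time from the landmark. Alternatively, enter the marker as a time-dependent covariate.
- For responder versus non-responder comparisons, use change at the same draw, before the first scan.

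Placing the landmark at a draw avoids doubt about patients whose progression is found on the week-12 scan. Section 2.4.2.1 gives 24 weeks for mononuclear-cell sampling against 12 weeks in 9.1 and 13.5; the two should be reconciled, because a longer window would widen the exposure.

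**Cost.** Wording only; no visit, sample or treatment changes. Patients who fail before the landmark leave these analyses. At medians of 2 to 6 months, a week-12 landmark keeps about 96 × 0.38 ≈ 36 to 96 × 0.73 ≈ 70 patients. The week-5 draw, 4 weeks after the first dose, keeps about 96 × 0.5^(4/8.7) ≈ 70 to 96 × 0.5^(4/26.1) ≈ 86 (2 and 6 months as 8.7 and 26.1 weeks), if all early failures are detected.

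### Section 13.5 names no adjustment for arm when relating on-treatment marker changes to outcome, so a marker that varlilumab shifts can look linked to outcome, or a real link can be hidden, if varlilumab also improves outcome

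*Combined protocol and SAP*

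**What the plan says.** Section 13.5 sets the scope: "In addition, baseline values and changes over time in each measure will be explored in relation to clinical outcome". It then names the methods. For response: "Differences between responders and non-responders will be assessed using Wilcoxon's rank sum (continuous data) or Fisher's exact (categorical data) test". For the time-to-event outcomes: "The relationship between each measure and time to event measures (PFS, OS) will be evaluated using Cox's proportional hazards models and log-rank tests". No covariate, stratum, by-arm analysis or interaction is attached to any of these, and the marker-specific bullets that follow add none.

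The one exception is the integrated biomarker, CD27 by IHC, when related to response. There the plan says "We will use logistic regression to model the response rate as a function of treatment and CD27 (as a continuous variable", and the curves are drawn separately for each arm.

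The on-treatment measures are chiefly the blood samples taken at baseline and every 14 days for 12 weeks, for CyTOF and a 30-cytokine panel. The CyTOF bullet also asks whether combinations of cell types predict outcome. The text never states that the arms will be pooled; it does not address arm at all.

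**The concern.** A two-sample rank test of responders against non-responders has no place for arm, so its natural reading is a single comparison over all patients. The protocol's own premises make arm a possible common cause of both sides of that comparison.

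- **Marker.** Sections 2.2.1 and 2.3.1 report that varlilumab lowered circulating regulatory T cells and raised inflammatory cytokines, and Section 2.4.2.4 names cytokines that are on the planned panel.
- **Outcome.** Section 13.1.3 is built on a response rate that rises with varlilumab.

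If both hold, responders come disproportionately from the combination arm, and so do shifted marker values. A marker that only records exposure to varlilumab could be reported as related to response. A marker that truly separates responders within each arm could be missed if varlilumab moves it the other way. Section 9.1 intends these studies to generate hypotheses, so the cost would be poor leads for later work.

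**Working it through.** **Inputs from the documents.** Section 13.1.3: "We will enter 48 evaluable patients on each group of the study using a 1:1 randomization scheme", and this "provides 80% power to detect an improvement in response rate from 25% to 45%, using a one-sided test at a significance level of 0.15". Section 13.1.5: the primary comparison is "performed using a one-sided Fisher's exact test at significance level 0.15". Section 13.5 states no significance level for the marker analyses.

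**Assumptions, because the documents give no figures.** Marker change is normal with SD 1 within arm. Varlilumab shifts its mean by d = 0.5 to 3 SD. Tests are two-sided at 0.05. Where a true within-arm association is assumed, it is 0.6 SD between responders and non-responders.

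**Step 1: the plan's own figure.** Sum Bin(x; 48, 0.25) × Bin(y; 48, 0.45) over all pairs (x, y) for which the one-sided Fisher p-value is below 0.15. The result is 0.809, which agrees with the stated 80%.

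**Step 2: size of the confounding.** With 1:1 allocation and no within-arm link:

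- Share of responders in the combination arm: 0.45 / (0.25 + 0.45) = 0.643.
- Share of non-responders in the combination arm: 0.55 / (0.75 + 0.55) = 0.423.
- Expected pooled difference, responders minus non-responders: d × (0.643 − 0.423) = 0.22d.

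If the response rates are equal, both shares are 0.5 and the difference is zero whatever the value of d.

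**Step 3: false positives, no within-arm link** (4,000 simulated trials per row; Monte Carlo standard error at most 0.8 points). Pooled is the Wilcoxon rank-sum test; stratified is the van Elteren test by arm.

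| Shift d (SD) | 0.22d | Pooled, 25% vs 45% | Stratified, 25% vs 45% | Pooled, 25% vs 25% |
|---|---|---|---|---|
| 0.5 | 0.11 | 7.5% | 4.8% | 5.2% |
| 1 | 0.22 | 14.1% | 4.4% | 5.0% |
| 1.5 | 0.33 | 24.6% | 5.2% | 5.2% |
| 2 | 0.44 | 31.2% | 4.9% | 4.7% |
| 3 | 0.66 | 41.2% | 4.8% | 5.2% |

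Repeat runs put the 2 SD figure between 31% and 34%. At a smaller benefit, 25% vs 35%, the pooled rate is about 8% at 1 SD and 12% at 2 SD.

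**Step 4: a true within-arm association of 0.6 SD, response 25% vs 45%.** When it runs against the shift, the expected pooled difference is −0.6 + 0.22 × (d + 0.6 × 0.20). At d = 2 that is −0.6 + 0.22 × 2.12 = −0.13, so most of the signal is cancelled.

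| Shift d (SD) | Opposite sign: pooled | Opposite sign: stratified | Same sign: pooled | Same sign: stratified |
|---|---|---|---|---|
| 0.5 | 51.0% | 74.6% | 85.5% | 74.5% |
| 1 | 25.2% | 72.2% | 91.3% | 74.3% |
| 1.5 | 10.7% | 72.8% | 92.6% | 73.3% |
| 2 | 5.0% | 72.4% | 91.8% | 73.5% |

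Here d is the difference between arm means. If d is instead taken between patients with the same response status, the opposite-sign pooled figures rise a little, to 57% at 0.5 SD and 14% at 1.5 SD. The higher same-sign pooled rates are not a gain, because part of the difference being detected is the arm difference.

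Masking does not need a treatment effect on response. At 25% in both arms, pooling adds d²/4 to the marker variance, and power is 57% at 1 SD and 37% at 2 SD, against 66% and 68% stratified.

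**Step 5: time to event.** With exponential times, no censoring, an assumed hazard ratio of 0.6 and a marker unrelated to outcome within arm, an unadjusted Cox score test is positive in 17.8% of trials at 1 SD and 40.1% at 2 SD. Stratified by arm it stays at about 5%. At a hazard ratio of 1.0 there is no inflation.

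**The case against.** **The plan is silent on arm; it does not prescribe pooling.** A statistician could analyse by arm without departing from Section 13.5. This stands, and the point is conditional for that reason. But the same section names treatment for CD27 against response, and Sections 13.4.1 to 13.4.3.1 name between-arm comparisons, so the omission elsewhere leaves the choice open until the data are seen.

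**A reader might infer that any marker varlilumab moves will look predictive.** The documents and the arithmetic do not support that. The false association needs varlilumab to change outcome as well as the marker. With equal response rates the error stays near 5%, and even at a 3 SD shift under the full design difference it is 41%.

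**A reader might extend the point to every marker other than CD27.** It does not reach baseline measures. For 9p24.1 FISH the plan says "The proportion of patients in each of these groups who achieve a response will be evaluated"; that category comes from tissue that is mandatory at baseline, and mutation burden is assessed before treatment. Both are fixed before randomisation, so arm cannot cause them. Later tissue is mandatory only for patients who cross over at progression and is otherwise optional, so the point applies chiefly to serial blood CyTOF and cytokines.

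**No decision rests on these tests.** Sections 2.4.2.1 to 2.4.2.5 label them mainly exploratory and descriptive, and only CD27 is tied to thresholds for later trials. This stands and lowers the severity. Multiplicity is also the larger source of false leads: with 30 independent null tests at 0.05 the chance of at least one positive is 1 − 0.95^30 = 0.785, and stratifying does not change that (real cytokines are correlated, so the figure is illustrative). Neither argument makes an arm-confounded comparison sound.

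**Stratifying has a small price.** With no shift, pooled power for the 0.6 SD association is about 78%, against 74% stratified.

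**Conclusion.** The concern holds in a limited form. As named, the tests of on-treatment marker change against response, PFS and OS take no account of arm. If they are run on both arms together under the trial's own alternative, false positives rise from about 5% to about 14-34% for shifts of 1 to 2 SD. A true 0.6 SD association opposed to a shift of that size falls from about 73% power to between 5% and 25% (Step 4 coding). All of this rests on assumed shifts, an assumed association and an assumed two-sided 0.05 level; the false-positive part also requires varlilumab to improve outcome.

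Two limits apply. The documents do not establish that the arms will be pooled. And an arm-stratified test would show only average association with outcome within arm; it could not show that a marker predicts benefit from varlilumab. Because the analyses are exploratory, this is a change to consider, not one that threatens the trial's main conclusions.

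**What to change.** In Section 13.5:

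- State that every analysis of on-treatment marker change against outcome is stratified or adjusted by randomised arm: van Elteren for continuous measures, Cochran-Mantel-Haenszel for categorical ones, and Cox models and log-rank tests stratified by arm.
- Report the estimates for each arm alongside the stratified result.
- Reserve any statement that a marker predicts benefit from varlilumab for a marker-by-arm interaction on a baseline marker.

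The cost is a few sentences. Randomised arm is already recorded, so no new data or samples are needed. The price is the slight loss of power noted above for a marker that varlilumab does not move.
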